Aim 2: Explore the impact of surgical weight loss on DSP outcomes (non-randomized). We hypothesize that bariatric surgery patients will have better DSP outcomes compared to patients without surgery, but the effect will be less than the effect of HIIT. To test this hypothesis, we will stratify the HIIT randomization in Aim 1 1:1 for those that have and those that do not have surgery. This will allow us to explore the effect of surgical weight loss on DSP outcomes without requiring an expensive, randomized, surgical intervention trial. Linear mixed models will determine the longitudinal effect of surgical weight loss on DSP. We will also assess the interaction between HIIT and surgical weight loss to evaluate the combined effect of these two interventions.

Impact: We will determine whether HIIT and/or surgical weight loss are promising disease modifying treatments for DSP. If successful, our phase 2 trial will form the basis of a large, pivotal phase 3 trial of exercise and/or weight loss for the treatment of DSP. Either would be the first disease modifying therapy for this common, highly morbid condition.

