on the primary outcome variable. The primary exposure variables are HIIT: yes/no (Aim 1), and bariatric surgery: yes/no (Aim 2). We will adjust for demographic, clinical, and baseline characteristics as covariates in the model. In addition to the main effects of HIIT exercise program and bariatric surgery, we will also examine selected interactions based on *a priori* considerations. In particular, we will focus on the interaction between HIIT and bariatric surgery to assess if the effect of HIIT exercise on IENFD is modified by bariatric surgery. Linear mixed effects regression modeling will be used to determine the relationship between the primary exposure variables and IENFD over time. Longitudinal data analysis approaches such as this offer enhanced statistical power, as subjects are able to serve as their own reference. Furthermore, linear mixed effects regression offers a flexible framework to handle missing data such as due to attrition. Let Y_{it} denote the IENFD of the *i*th patient at the *t*th time point. Then Y_{it} can be modeled using the random intercept model.¹¹⁴ The random intercept model can be viewed as arising from a two-stage model as follows:

Stage 1: subject-specific trajectory: $Y_{it} = \mu_{0i} + \lambda' Z_i + \underline{\theta' X}_{it} + \underline{e}_{it}$

Stage 2: between-subjects: $\mu_{0i} = \beta_{00} + \beta_{0i}$

Combining the two stages, we can write $Y_{it} = \beta_{00} + \beta_{0i} + \theta' X_{it} + e_{it}$

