where β_{00} is the population-averaged intercept, Z_i is the matrix of main effects and interaction corresponding to HIIT exercise and bariatric surgery, \underline{X}_{it} is the matrix of fixed covariates (demographic and baseline characteristics), λ and θ are the vectors of corresponding fixed effects parameters, β_{0i} is the subject-specific random (intercept) effect capturing heterogeneity across subjects due to unmeasured confounders, and en is the random error characterizing variation due to sources like within-subject fluctuations and measurement error. The random effect β_{0i} is assumed to follow a normal distribution with mean zero and variance σ^2_{sub} , and the eit's are assumed to be distributed normally with mean **0** and variance covariance matrix R (non-diagonal). Furthermore, we also assume that θ_{0i} and e_{it} are independent. Maximum likelihood method will be used to estimate the model parameters. We will use Akaike Information Criterion (AIC) and Schwarz Bayesian Information Criterion (BIC) to guide the selection of the covariance structure. Inference for λ (which is of primary interest) will be based on Wald tests. We will use PROC MIXED in SAS to fit the above model. To explore potential non-linear or threshold effect of treatment exposure on IENFD we will use a nonparametric regression model fitted using the framework of generalized additive models (GAM). 115 Given the exploratory nature of the research proposed here, the GAM models will allow us the flexibility to include a smooth functional term instead of restricting to a linear relationship. The smoothing term is fitted by using penalized regression splines or locally smoothed loess curves, with the degree of smoothness chosen in a data-adaptive way, using cross-validation techniques. We will use the gam function in the mgcv package available in the R software to fit these non-parametric regression models. We will perform sensitivity analyses to assess how subjects who withdrew affect conclusions of the analysis. An intent-to-treat analysis set (including subjects who are randomized, treated, and have a baseline IENFD) will be used to assess treatment effects, with multiple imputation methods¹¹⁶ employed to impute outcomes for subjects with missing post-baseline data. Depending on the extent and pattern of missingness, other simpler sensitivity analyses may be used: e.g., subjects completing the study (completers) may be analyzed using a repeated measures analysis of variance model. The model will include the same covariates that are included in the primary analysis.

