
C3.7.2 Analyses of secondary outcomes: Due to the pitfalls of multiple testing, formal statistical testing won't be performed. For analysis of repeated measures of continuous data (CCM, cardiovascular reflex tests, MNSI, UENS, mTNS, SAS, McGill Pain questionnaire, NeuroQOL, and functional assessments), the longitudinal approaches described above will be employed. Specifically, each outcome will be analyzed separately using a linear mixed effect regression model, with the treatment group as the primary exposure.

C3.7.3 Exploratory analyses: To investigate the potential modifying effects of sex, we will perform an additional analysis that includes an interaction term between the intervention groups and sex. Similarly, we will explore the differential effect of sleeve gastrectomy versus Rou-en-Y gastric bypass by including separate indicator variables for these two different surgical techniques. We will also investigate the potential weight loss independent effects of bariatric surgery by evaluating the earliest time point (3 months). In addition to other metabolic syndrome components, we will study the effect of change in insulin sensitivity as measured by OGIS on our primary outcome. Finally, we will perform an analysis of those who complete more than 80% of supervised exercise sessions to assess the effect of exercise compliance. Importantly, these analyses will be hypothesis generating for future studies.

C3.8. Power calculation: The purpose of this clinical trial is to provide the preliminary data necessary to design a multicenter clinical intervention trial. Therefore, it is not strictly amenable to formal power

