considerations. However, there are two assumptions necessary to justify the multicenter trial. The first is that HIIT will cause an increase in IENFD (re-innervation) and the second is that the natural progression of DSP is loss of nerve fibers over time. The primary outcome is an assessment of IENFD at the proximal thigh over 4 time points spanning 24 mo in the four trial arms. To estimate the likely effect sizes of the four interventions, we will rely on previous well-conducted studies, including our ongoing NIH K23 project. For the routine exercise/no surgery group, we estimate that the IENFD will decrease similar to that observed for those with pre-diabetes and DSP. Over 26.7 mo, IENFD at the proximal thigh decreased from 19±5 to 13±4. Given that our population includes patients with normoglycemia, we expect a decline of at least 3 fibers/mm over the 2 yr of our study. For the HIIT/no surgery group, we estimate that the IENFD will increase by 1.4±2.3 fibers/mm based on a study of the effect of exercise by Smith et al.³⁰ They saw this effect after 1 yr, but we will conservatively estimate that the effect will plateau after the initial yr after the intervention. For routine exercise/surgery group, we estimate that the IENFD will increase by 0.2±7.0 based on our preliminary data on patients undergoing diet-induced weight loss for 2 yr. For the HIIT/surgery group, we estimate that the effect will be additive compared to the two separate interventions. With our expected sample size of 30 patients (allowing for ~15% attrition) in each of the four treatment groups, we will have at least 80% power to detect effect sizes between 0.9 and 1.7 as statistically significant based on a two-sided test with alpha=0.05.

- **C3.9. Data collection and management:** Data report forms will be filled out during each visit, verified, and entered into RedCap. Validation reports will be run, and checked for omissions, improbable values, and data consistency. Distributions of continuous measures will be assessed for symmetry and transformations will be applied as needed. Co-investigator [name], Professor of Biostatistics, [name], graduate student, and [name] will have data access for monitoring and verification.

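### The primary analysis (C3.7.1) puts the non-randomized surgery effect and the interaction level with the randomized HIIT effect, against the Aim 2 label, and names no confirmatory term

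*Protocol*

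**What the plan says.** In the protocol's Specific Aims, Aim 1 is the randomized efficacy question. Aim 2 is worded differently: "Explore the impact of surgical weight loss on DSP outcomes (non-randomized". The Aim 2 heading in section C2 repeats both labels.

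Section C3.7.1 does not keep this ranking. It states "The primary exposure variables are HIIT: yes/no (Aim 1), and bariatric surgery: yes/no (Aim 2", and adds that "we will focus on the interaction between HIIT and bariatric surgery". In the model, the design term multiplied by λ "is the matrix of main effects and interaction corresponding to HIIT exercise and bariatric surgery", and the rule for testing is "Inference for λ (which is of primary interest) will be based on Wald tests". It gives no order of testing, joint test, adjustment or single confirmatory coefficient.

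The one significance level in the protocol is in the power section (C3.8), which speaks of effects detectable as "statistically significant based on a two-sided test with alpha=0.05" with 30 patients in each of four groups. It names no contrast.

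Section C3.7.2 gives a reason for not testing secondary outcomes that begins "Due to the pitfalls of multiple testing, formal statistical testing". Section C3.7.3 holds a separate exploratory tier (sex, type of procedure, the 3-month effect, insulin sensitivity, compliance). Neither the surgery main effect nor the HIIT-by-surgery interaction is in it.

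**The concern.** The two parts of the protocol give the surgery comparison different standing. Under the aims it generates hypotheses; under C3.7.1 it has the same rank as the randomized comparison.

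This matters in three ways:

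- Surgery is self-selected, and C3.10.1 obtains consent only after the patient has decided about it. A significant surgery coefficient could therefore carry the primary result although randomization does not protect it.
- If more than one coefficient may support a claim, 5% no longer describes the error rate of the primary analysis. The protocol accepts this principle when it declines to test the secondary outcomes.
- Which HIIT effect answers Aim 1 is left open. With an interaction in the model, the coefficient called HIIT changes its meaning with the coding, and the protocol writes both factors as yes/no.

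**Working it through.** **Inputs.** Two exposures called primary and three terms in λ (C3.7.1); two-sided 0.05 and 30 evaluable patients per cell (C3.8). Assumptions: no true effects, equal cells, independent patients with common variance σ², no confounding, each term tested at 0.05.

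**The plan's own figure.** The protocol states no familywise error rate. Its only related figure is at least 80% power for effect sizes of 0.9 to 1.7. Read as standardised differences for 30 v 30, the 80% threshold is (1.96 + 0.84) × √(2/30) = 0.72. Power is 93.6% at 0.9 and above 99.9% at 1.7. The statement is therefore true as an inequality, but its ends are not reproduced as 80% thresholds. Nothing below depends on it.

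**What the coefficients estimate.** Write the cell means as m(HIIT, surgery), each with variance σ²/30.

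| Coding | HIIT coefficient | Standard error | Detectable at 80% power |
|---|---|---|---|
| 0/1 (yes/no) | m(1,0) − m(0,0): effect without surgery | σ√(2/30) = 0.258σ | 0.72 SD |
| Centred | mean of the effects in the two strata | σ√(2/60) = 0.183σ | 0.51 SD |

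The two rows are different estimands, based on about 30 v 30 and about 60 v 60 patients.

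**Correlation of the tests.** With centred coding and equal cells the three estimates are uncorrelated. With 0/1 coding:

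- HIIT and surgery share m(0,0): covariance σ²/30, variances 2σ²/30, correlation 1/2 = 0.5.
- The interaction is m(1,1) − m(1,0) − m(0,1) + m(0,0): variance 4σ²/30, covariance with each main term −2σ²/30, correlation −2/√(2 × 4) = −0.71.

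**Chance of at least one |z| > 1.96.**

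- HIIT or surgery: centred, 1 − 0.95² = 9.75%; 0/1 coding, 9.1% (simulation with the correlation above).
- HIIT, surgery or interaction: centred, 1 − 0.95³ = 14.3%; 0/1 coding, 11.3% (simulation).
- Bounds that hold for any correlation: 2 × 5% = 10% and 3 × 5% = 15%.
- With an assumed 2:1 split of surgical to non-surgical patients: 8.8% to 9.7% for two tests and 10.7% to 14.0% for three.

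**Alternatives.** One named contrast at 0.05 gives 5.0%. Bonferroni over two tests gives 1 − 0.975² = 4.94%, and over three 4.92%. At 30 v 30, Bonferroni lowers power at 0.72 SD from 80% to 71% or 66%.

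**The case against.** Several stronger readings are tempting, and the protocol does not support them.

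- A reader might infer that all three terms are each tested at 5%. C3.7.1 gives no level and does not say whether the Wald tests are separate, joint or ordered. The 0.05 comes from C3.8 and is not assigned to any term.
- A reader might apply a 9% error rate to all three tests. That figure belongs to two; three give about 11% to 14%.
- A reader might treat the interaction as a third route to success. C3.7.1 uses it to ask whether surgery modifies the HIIT effect, and a significant interaction alone is no efficacy claim.
- A reader might infer an either-one-wins rule. The Impact paragraph and section A4 say that either intervention could prove promising, but no success rule is stated.

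It can also be argued that two distinct interventions in a 2×2 layout need no familywise control, above all in a trial that C3.8 describes as supplying preliminary data. That question is debated, and leaving a long list of secondary outcomes untested while testing a few terms on one outcome is not inconsistent in itself. Finally, alpha allocation is often left to the SAP, which is not at hand.

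These arguments lower the weight of the error rates. They do not remove the conflict between the Aim 2 title and C3.7.1, which the protocol itself states. The remark in C3.7.1 on the exploratory nature of the research serves to justify the additive models and does not rank the Wald tests.

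**Conclusion.** The concern holds as a contradiction in the protocol, with a conditional error rate attached. Surgery is exploratory in the aims and primary in C3.7.1, and no term of λ is named as confirmatory. If HIIT and surgery are each tested at two-sided 0.05, the chance of at least one false positive is about 9% to 10%. It is about 11% to 14% only if the interaction is also counted as a claim. These rates assume no true effects and no confounding. Residual confounding could raise the rate for the surgery term above 5%, by an amount that the documents do not allow one to compute.

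The coding point does not depend on any view about multiplicity: under yes/no coding with an interaction, the HIIT coefficient does not estimate the Aim 1 effect across the randomized population.

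**What to change.** In C3.7.1, name the randomized HIIT contrast, averaged over the surgery strata, as the single confirmatory test at two-sided 0.05, and define it as a contrast so that it does not depend on the coding. State that the surgery effect and the HIIT-by-surgery interaction are exploratory and will be reported as estimates with 95% confidence intervals and no significance claim, in line with the Aim 2 title. Make the change before the outcome data are analysed, and carry it into the SAP.

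The cost is a few sentences and the loss of a formal significance claim for Aim 2. No alpha is split. It should not be said that Aim 1 power stays the same: that depends on which HIIT contrast the protocol meant, since the averaged contrast uses about 60 v 60 patients and the yes/no coefficient about 30 v 30. If the sponsor wants a formal claim for surgery as well, the protocol must say so and state how alpha is shared, at the loss of power shown above.

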those that do not have surgery. We will also stratify by glycemic status to limit confounding. Randomization will be performed using permuted blocks, with a block size known only to the statistician. We will perform longitudinal analyses using linear mixed models to study the evolution of IENFD from baseline to 2 yr (4 measures in total). We will compare the effect of HIIT, bariatric surgery, and the combination of HIIT and surgery on all outcomes.

C1. Aim 1: Examine the efficacy of a HIIT exercise regimen on DSP outcomes (randomized)

C1.1. Introduction: There is an urgent need for a disease modifying therapy for the prevention and treatment of DSP. Currently, physicians only have neuropathic pain medications and glucose control to offer patients with DSP.^{7, 27} However, glucose control alone is not effective at preventing DSP and many patients with diabetes develop DSP despite good glucose control.²⁷ Similarly, no disease modifying interventions exist for the increasing population with pre-diabetes and/or obesity. Thus, it is essential to identify new interventions that can prevent and treat DSP. To date, uncontrolled studies support improvement in the natural history of DSP decline over time after an exercise intervention.²⁸⁻³⁰ The next step is to determine whether a randomized, intensive, exercise intervention improves DSP outcomes compared to routine exercise counseling.

C1.2. Justification & feasibility:

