| Anthropometric measures^ | | X | X | X | X |
| Orthostatic Hypotension Assessment [^] | | Х | X | X | Х |
| Quality of Life measures: | | | | | |
| NeuroQol | | X | X | X | X |
| Questionnaires | | X | Х | Х | X |
| Demographics | | X | | | |
| Functional Assessments | | | , . | , . | |
| Berg Balance Scale [^] | | X | X | X | X |
| 8-foot Get Up and Go Test^ | | X | X | X | X |
| Modified Falls Efficacy Scale | | Х | X | Х | Х |
| Aerobic Assessment | | | | | |
| VO2 max | X | | | | X ⁺ |
| | | | | | |
| Dual Energy X-ray Absorptiometry | | | | | |
| Duai Lineigy A-iay Absorptionietry | | X | | | X |

^{*}Randomization to exercise protocol to occur after baseline visit

Data collected for clinical purposes as part of the Adult Bariatric Surgery Program will be reviewed as part of this study and included in the study records.

- **C3.6. Timeline and milestones:** The planned study duration is 5 yr, with 2 yr of subject accrual, 2 yr of subject follow-up, plus 1 yr for analysis and results presentation.
- **C3.7. Statistical analysis:** The four treatment groups (HIIT/no surgery, HIIT/surgery, routine exercise/no surgery, routine exercise/surgery) will be compared with respect to demographic and baseline variables (e.g., age, sex, glycemic status, OGIS, BMI, etc.). If a significant difference is found in any variable, the models described below will be fitted after adjusting for these variables.
- C3.7.1 Analysis of primary outcome: The primary outcome is IENFD at the proximal thigh, measured at baseline, 3, 12, and 24 mo. Exploratory analysis will be performed to assess the need for any transformation

^{*}Only participants randomized to the HIIT will complete a second time

 $^{^{\}mathsf{T}}$ Participants can consent to have skin biopsy added to biorepository

[^]Participants may complete the consent and outcomes virtually prior to the upcoming visit to decrease in-person interaction due to Covid-19. If the outcome cannot be completed successfully it with be completed during the visit.

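### The primary model treats baseline IENFD as a response but gives HIIT and surgery only time-constant terms, so the tested HIIT coefficient averages in a visit with no effect and baseline gaps can enter the surgery coefficient

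*Protocol*

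**What the plan says.** Protocol section C (Approach) says the linear mixed models are "to study the evolution of IENFD from baseline to 2 yr (4 measures in total"). C3.7.1 repeats the schedule: "The primary outcome is IENFD at the proximal thigh, measured at baseline, 3, 12, and 24 mo". The response Y_it is the IENFD level at each time point, not a change.

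The Stage 1 equation in C3.7.1 is Y_it = μ_0i + λ'Z_i + θ'X_it + e_it. Z_i carries no time index and "is the matrix of main effects and interaction corresponding to HIIT exercise and bariatric surgery". X_it does carry one, but it "is the matrix of fixed covariates (demographic and baseline characteristics"). Inference is on λ, "which is of primary interest) will be based on Wald tests". On software the text says: "We will use PROC MIXED in SAS to fit the above model". AIC and BIC are used "to guide the selection of the covariance structure".

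On adjustment, C3.7.1 says: "We will adjust for demographic, clinical, and baseline characteristics as covariates in the model". It does not say whether baseline IENFD is among them. C3.7 adds that any variable differing significantly between the four groups at baseline will be adjusted for. The footnote to Table 6 places randomisation after the baseline visit.

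**The concern.** Before randomisation HIIT cannot have an effect, so the expected HIIT-minus-control difference at baseline is zero. A HIIT term that is constant over all four visits has to average that zero with the three post-baseline differences. The tested coefficient is then neither the change from baseline that section C sets out to study nor the post-baseline effect.

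Surgery is not randomised, so its baseline difference need not be zero. A constant surgery term absorbs a pre-existing gap as if it were an effect. C6 says the results will inform which intervention or interventions go to phase 3, so both estimates matter.

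**Working it through.** **The plan's own figure.** C3.8: 35 × 0.85 = 29.75, about 30 per group. For a simple two-group comparison at two-sided 0.05, 30 per group gives 94% power at a standardised effect of 0.9 and over 99% at 1.7. The stated minimum of 80% is therefore true as a lower bound. It says nothing about λ.

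**Inputs (C3.8).** Routine exercise/no surgery: −3 over 24 months. HIIT/no surgery: +1.4 by 12 months, then flat. Routine exercise/surgery: +0.2 over 24 months. Assumed here: linear change between these points and complete data.

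**HIIT minus control, no-surgery stratum**

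| Month | HIIT | Control | Difference |
|---|---|---|---|
| 0 | 0 | 0 | 0 |
| 3 | 0.35 | −0.375 | 0.725 |
| 12 | 1.4 | −1.5 | 2.9 |
| 24 | 1.4 | −3 | 4.4 |

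Under a random intercept or compound symmetry, all visits have equal weight:
- Coefficient: (0 + 0.725 + 2.9 + 4.4)/4 = 2.01.
- Post-baseline average: (0.725 + 2.9 + 4.4)/3 = 2.675.
- Ratio: 0.75.

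If HIIT works equally in both surgery strata, the averaged effect is the same. If instead the quoted changes add (HIIT/surgery 1.4 + 0.2 = 1.6), the averaged differences are 0, 0.5375, 2.15 and 2.9. The coefficient is then 1.40 against a post-baseline average of 1.86, again a ratio of 0.75.

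**Other covariance structures.** The visit weights are V⁻¹1/(1'V⁻¹1). For AR(1) by visit the baseline weight is 1/(4 − 2ρ) and the coefficient is [(1 − ρ)(0.725 + 2.9) + 4.4]/(4 − 2ρ). At ρ = 0.5 these are 0.33 and 2.07. AR(1) by visit or by elapsed time, over the correlations tried, gives coefficients of about 2.0 to 2.4. With the protocol's random intercept carrying 80% of a correlation of 0.848, the baseline weight is 34% (by visit) or 40% (by time).

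**Effect of a baseline covariate, Aim 1.** With baseline IENFD as a covariate and still a response, estimate and standard error both shrink by 3/4, so the test is that of the baseline-adjusted post-baseline average. Only the dilution remains.

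**Power if baseline IENFD is left out.** With level SD s and change SD c, ρ = 1 − c²/(2s²). For 60 v 60:
- SE as written: s√[(1 + 3ρ)/4 × 2/60].
- SE of the baseline-adjusted post-baseline average: s√[((1 + 2ρ)/3 − ρ²) × 2/60].

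The level SDs 12.7 and 5.4 are the two obese columns of Table 5; 5 and the change SDs 7.0 and 2.3 are from C3.8. Targets are 2.01 and 2.675 (same HIIT effect in both strata).

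| s | c | ρ | SEs | Power as written | Power, adjusted average |
|---|---|---|---|---|---|
| 12.7 | 7.0 | 0.85 | 2.18 / 0.98 | 15% | 78% |
| 5.4 | 7.0 | 0.16 | 0.60 / 0.63 | 92% | 99% |
| 5 | 7.0 | 0.02 | 0.47 / 0.54 | 99% | >99% |
| 5 | 2.3 | 0.89 | 0.88 / 0.33 | 63% | >99% |

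These pair SDs from different cohorts, so they show the range and nothing finer.

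**Aim 2.** Surgery minus no surgery, without HIIT: 0, 0.4, 1.6, 3.2. The coefficient is 5.2/4 = 1.3. A persistent baseline gap of 1.3 fibers/mm, unadjusted, would produce the same coefficient with no surgery effect. With s = 5 and 60 v 60, the SE of a baseline difference is 5√(2/60) = 0.91, so a gap of 1.3 gives z = 1.42 and would not count as significant in a simple two-group comparison.

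With baseline IENFD as a covariate, the slope of the four-visit mean on baseline is (1 + 3ρ)/4, so 3(1 − ρ)/4 of the gap remains: 11% at ρ = 0.85 and 63% at ρ = 0.16.

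**The case against.** **Is baseline really a response?** C3.7.1 requires a baseline IENFD for the analysis set and imputes missing post-baseline data, which would fit a post-baseline response. But section C ties the four measures to the mixed model, and nothing removes baseline from Y_it.

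**Is this for the SAP?** Visit coding often is. Here the protocol writes the model, names the tested parameter and says that model will be fitted. C3.7.1 leaves room for further interactions, but the one it singles out is HIIT by surgery. A visit main effect placed in X_it would not stop the averaging.

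**Is Aim 2 protected?** Partly. The C3.7 rule would catch a significant baseline gap. It misses a non-significant one, and adjustment leaves a residue while baseline stays a response. Aim 2 is also labelled exploratory.

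A reader might infer more than the document supports:
- *That the HIIT test is invalid.* It is not; randomisation keeps its type I error.
- *That power is certainly poor.* The loss depends on leaving out baseline IENFD and on a correlation the protocol does not give.
- *That the HIIT effect is more than halved, 2.0 against 4.4.* That compares with Month 24 alone. An average over post-baseline visits is a legitimate target, and the like-for-like figure is 2.7.
- *That the covariance choice makes the estimate arbitrary.* With the C3.8 changes it moves only between about 2.0 and 2.4. Baseline weights near one half require almost no random-intercept variance.
- *That treatment is missing from the model.* The combined equation omits λ'Z_i, but λ is defined and tested, so this is a notation slip.
- *That the HIIT coefficient applies only without surgery.* That holds under 0/1 coding, which the protocol does not state.

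**Conclusion.** The point holds and should be fixed. As written, the HIIT coefficient includes a visit at which the effect is zero by design. It is 3/4 of the average post-baseline effect under a random intercept or compound symmetry with complete data, which is about 2.0 against 2.7 fibers/mm on the C3.8 figures with linear interpolation. In Aim 1 this is dilution of the estimate, with no false-positive problem; lost power is a further cost only if baseline IENFD is not a covariate. In Aim 2 a baseline gap of about 1.3 fibers/mm could pass the C3.7 rule unadjusted and equal the whole expected surgery coefficient. If it is adjusted for while baseline stays a response, 3(1 − ρ)/4 of it still remains.

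**What to change.** Add categorical visit, HIIT × visit and surgery × visit terms, with HIIT × surgery × visit for the interaction question. Then choose one handling of baseline and state it:
- keep baseline as a response, with HIIT and control baseline means constrained equal within each surgery stratum; or
- model only the 3, 12 and 24 month values, with baseline IENFD as a named covariate.

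Name the primary HIIT contrast (Month 24 or the post-baseline average), averaged over surgery strata. Estimate surgery as change from baseline. Restore λ'Z_i in the combined equation as a notation correction.

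The cost is revised wording, a few lines of PROC MIXED code and a few more fixed-effect parameters. No new visits or data are needed. A Month 24 contrast uses fewer measurements than an average, so that choice should follow the question asked.

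### The random intercept does not deal with unmeasured confounding of surgery: as written, the Aim 2 coefficient compares average IENFD levels and carries any stable group difference the covariates leave unexplained

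*Protocol*

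**What the plan says.** Aim 2 is labelled exploratory and non-randomized. Its stated attraction is: "This will allow us to explore the effect of surgical weight loss on DSP outcomes without requiring an expensive, randomized, surgical intervention trial". Under C3.10.1, patients consent after they have decided for or against surgery.

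C3.7.1 sets out the model:

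- **Response.** "The primary outcome is IENFD at the proximal thigh, measured at baseline, 3, 12, and 24 mo". Baseline is thus one of the four responses.
- **Exposure.** The matrix Z, indexed by patient only, "is the matrix of main effects and interaction corresponding to HIIT exercise and bariatric surgery". Inference is on its coefficients λ ("which is of primary interest) will be based on Wald tests").
- **Random intercept.** It is called the "random (intercept) effect capturing heterogeneity across subjects due to unmeasured confounders", and it "is assumed to follow a normal distribution with mean zero and variance" common to all patients. Only its independence from the error term is spelled out.
- **Covariates.** "We will adjust for demographic, clinical, and baseline characteristics as covariates in the model". C3.7 adds any baseline variable that differs significantly among the four groups. Baseline IENFD is not named.

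No time term and no surgery-by-time term is written. The covariate matrix carries a time index but is described as demographic and baseline characteristics. The combined equation drops the λ term; I use the Stage 1 line, which has it.

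**The concern.** A confounder of surgery is, by definition, distributed differently in patients who do and do not have surgery. An intercept with the same distribution in both groups cannot represent it. The independence from surgery is not stated in words, but it follows from the single mean-zero distribution and the maximum likelihood fit.

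The clause matters because of what surrounds it. With a time-constant surgery indicator, baseline among the responses and no surgery-by-time term, the tested coefficient is a contrast of levels between self-selected groups. The protocol elsewhere aims at the evolution of IENFD from baseline (section C) and says that subjects act as their own reference (C3.7.1). For an exposure that is constant within a patient, the written coefficient delivers neither.

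The central hypothesis ranks HIIT above surgery, and C6 says the results will decide which intervention goes into phase 3. The surgery coefficient is one side of that comparison.

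**Working it through.** **Stated figure.** The protocol gives none to reproduce here; the point concerns what the model estimates.

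**Inputs from the protocol.** 30 evaluable patients in each of four groups (C3.8), so 60 with and 60 without surgery; four visits. SDs of thigh IENFD level run from 4 (C3.8) to 12.7 (Table 5, obese without neuropathy). The expected changes of +0.2 (routine exercise/surgery) and −3 (routine exercise/no surgery) differ by 3.2 fibers/mm (C3.8).

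**Assumptions.** The protocol gives no baseline difference between surgery groups and no within-patient correlation ρ. I borrow 3.2, and half of it (1.6), as illustrative stable differences δ. I take two settings: SD 12.7 with ρ 0.85, and SD 7.0 with ρ 0.5. C3.8 gives 7.0 as an SD of change; I use it as a level SD because it lies between 4 and 12.7.

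**Step 1: what the coefficient estimates.** With complete data and an exchangeable covariance, the fitted surgery coefficient is the difference in patients' four-visit means. If surgery has no effect but the groups differ by δ at every visit, its expectation is δ. Another covariance structure reweights the visits, but the weights still sum to one, so δ passes through whole. A visit main effect alone does not change this.

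**Step 2: does the random intercept absorb any of it?** The written model was fitted to simulated data with no true surgery effect (no covariates, between- and within-patient SD 4 each, 150 runs per row):

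| Stable difference | Estimate, model as written | Rejection | Estimate, surgery × post-baseline | Rejection |
|---|---|---|---|---|
| 0 | −0.08 | 8% | −0.02 | 5% |
| 1 | 1.05 | 24% | −0.01 | 6% |
| 2 | 2.07 | 72% | 0.13 | 4% |
| 3 | 3.10 | 94% | 0.01 | 6% |

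The predicted intercepts had the same average in both surgery groups (difference 0.00), so they absorbed nothing. The HIIT coefficient stayed between −0.07 and 0.09.

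**Step 3: false-positive rate without covariates.** SE = √[SD² × (1 + 3ρ)/4 × 2/60].

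- SD 12.7, ρ 0.85: √(161.29 × 0.8875 / 30) = 2.18. For δ = 3.2, z = 1.47 and rejection is 31%; for δ = 1.6, 11%.
- SD 7.0, ρ 0.5: √(49 × 0.625 / 30) = 1.01. For δ = 3.2, z = 3.17 and rejection is 89%; for δ = 1.6, 35%.

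Simulation with 3,000 trials per setting gave 29.4%, 11.4%, 87.9% and 34.2%.

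**Step 4: baseline IENFD as a covariate.** On post-baseline visits the carry-over is (1 − ρ)δ. For δ = 3.2 that is 0.15 × 3.2 = 0.48 or 0.5 × 3.2 = 1.6. If baseline also stays among the four responses, three quarters of that remains: 0.36 or 1.2. Simulated rejection for δ = 3.2 fell to about 7% and 47%, and for δ = 1.6 to 4% and 16%.

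**Step 5: dilution of a real effect.** Averaging in baseline keeps 3/4 of a constant post-baseline effect. With a true surgery effect of 3.2 and δ = 2, the expected coefficient is 2 + 0.75 × 3.2 = 4.4. The simulation gave 4.35, and the surgery × post-baseline contrast gave 3.18.

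**The case against.** The strongest reply is that the protocol does adjust. C3.7.1 includes demographic, clinical and baseline characteristics, and C3.7 adds baseline variables that differ. This stands in part. A reader might infer that every stable difference between the surgery groups lands in the coefficient. The document does not support that; only the part the measured covariates leave unexplained does. If baseline IENFD counts as a baseline characteristic, Step 4 shows a clear reduction, though not to zero. The significance screen is weak protection: a two-group test at 60 versus 60 finds a difference of 3.2 only 28% (SD 12.7) to 71% (SD 7.0) of the time.

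Other points for the protocol:

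- **Design.** All patients come from a bariatric clinic under one BMI rule, must have started the surgical process, and are excluded if not surgical candidates for medical or psychiatric reasons. This narrows selection but does not remove it.
- **Wording.** The clause speaks of capturing heterogeneity and nowhere says that confounding is controlled. Likewise, a reader might take "We will also stratify by glycemic status to limit confounding" as a claim to protect Aim 2. Stratifying the HIIT randomization balances HIIT against counseling, not surgery against no surgery, but the protocol does not clearly claim otherwise.
- **Status.** Aim 2 is exploratory. That limits the consequence without making the coefficient right.
- **Alternative analysis.** Change from baseline and baseline adjustment rest on different untestable assumptions in non-randomized groups. The near-zero estimates in Step 2 arise because the simulated difference was perfectly stable.
- **Unseen analysis plan.** Time terms may be given there. The protocol nevertheless writes out a model and names λ as the target, and that model needs correcting.

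**Conclusion.** The point holds for Aim 2. The random intercept as defined removes no confounding of surgery. The written coefficient is a difference in average level whose bias equals the stable difference left unexplained by the covariates. Under an exchangeable covariance and complete data, it also shrinks a constant post-baseline effect to three quarters.

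The size of the bias in this trial is unknown, because the protocol gives no baseline surgery difference. The 30% to 90% range belongs to an unadjusted difference of 3.2 with assumed SDs and correlations. It should not be read as the trial's error rate; with baseline IENFD as a covariate the same settings give about 7% to 47%.

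Nor should the point be extended to a confounded HIIT comparison. HIIT is randomized, and its coefficient shows no such bias. It does share the dilution: in the Step 5 simulation a true HIIT effect of 4.4 was estimated at 3.19.

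**What to change.** In C3.7.1:

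1. Remove the reference to unmeasured confounders and describe the random intercept as between-subject heterogeneity.
2. Keep baseline IENFD as a response. Add visit and surgery-by-visit terms, with the baseline surgery term left free. Do not force equal baseline means across surgery groups.
3. Define the Aim 2 effect as the surgery minus no-surgery difference in change from baseline, and keep the measured covariates, including glycemic status, in the model.
4. Report the baseline difference between the surgery groups.
5. State that the contrast assumes parallel trends without surgery and that time-varying confounding remains. A baseline-adjusted analysis can be an optional sensitivity check.

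The cost is a change of wording and a few model terms. All four biopsies are already scheduled, so no new data are needed.
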